#### **4.7.3            Laboratory Data**

Laboratory data with values outside of the normal ranges will be identified. Laboratory values will be summarized by treatment arm and grade using the NCI-CTCAE version 4.03 grading system. Shift tables will be used to present the number and percentage of patients with values within, above, or below the normal range comparing baseline to subsequent assessments by treatment arm.

Nadir is defined as the lowest value observed in the interval between Cycle 1, Day 1 up to and including predose on Cycle 2, Day 1. If there is no Cycle 2, Day 1 value, and the interval between Cycle 1 Day 1 and Cycle 2 Day 1 is not definable then the latest value in Cycle 1 will be used to define the interval. If no

value is lower than baseline (i.e., Cycle 1, Day 1 cannot be the nadir), then the nadir does not exist, and the patient is excluded from the analysis.

For all patients summary statistics and boxplots for time to nadir (in days) will be produced by treatment arm, as well as Kaplan Meier for time to nadir starting on study drug first administration.

Time to recovery is defined as the time until the value crossed back up and over 100 for platelets and over the thresholds 0.5 or 1 for neutrophils after the interval between Cycle 1, Day 1 and the predose on Cycle 2, Day 1. If there is no Cycle 2, Day 1 value, then the latest value in Cycle 1 will be selected. Patients receiving a transfusion within 24 hours prior to the laboratory assessment selected will be excluded.

For responders only (CR, CRp, CRi), summary statistics and boxplots for time to recovery (in days) for both neutrophils and platelets will be produced by treatment arm, as well as Kaplan Meier for time to recovery starting on study drug first administration.

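### SAP 4.7.3 looks for count recovery after the Cycle 1 interval instead of within it, and excludes transfused patients instead of transfusion-affected values

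*SAP*

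**What the plan says.** SAP section 4.7.3 (Laboratory Data) describes two summaries of blood counts.

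- **Nadir:** "Nadir is defined as the lowest value observed in the interval between Cycle 1, Day 1". This window closes with the predose sample of Cycle 2 Day 1.
- **Recovery, thresholds:** "Time to recovery is defined as the time until the value crossed back up and over 100 for platelets". Two cut-offs, 0.5 and 1, are given for the neutrophil count.
- **Recovery, window:** the crossing is located "after the interval between Cycle 1, Day 1 and the predose on Cycle 2, Day 1".
- **Recovery, fallback:** "If there is no Cycle 2, Day 1 value, then the latest value in Cycle 1 will be selected".
- **Recovery, transfusions:** "Patients receiving a transfusion within 24 hours prior to the laboratory assessment selected will be excluded".

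The recovery summary is restricted to responders (CR, CRp and CRi). It is presented by arm with descriptive statistics and boxplots, "as well as Kaplan Meier for time to recovery starting on study drug first administration". The section gives no censoring rule for patients who never cross the threshold.

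**The concern.** The nadir is sought inside the interval from Cycle 1 Day 1 to Cycle 2 Day 1. The recovery that follows it is sought after that same interval. For a patient who receives Cycle 2, the search therefore opens as the next myelosuppressive cycle starts. In a CR, the induction recovery has already happened by then.

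The transfusion rule adds a second difficulty. It removes patients because of something that happens after randomization and is related to the outcome being measured.

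The summary bears on a risk that the protocol takes seriously. Section 4.4.2.3 warns of potentially prolonged thrombocytopenia, and section 5.1.1.2 says that adding idasanutlin to cytarabine may lengthen aplasia. A by-arm description of recovery time is one of the places where a reader would look for that effect. It should measure induction recovery, and measure it in the same way for every responder.

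**Working it through.** The SAP states no numerical target for this summary, so there is no figure to reproduce. The check compares the texts, applies the rule to an example, and counts how many CRs the plan expects.

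**1. When recovery happens in a CR.**
- Protocol section 4.5.8: CR needs ANC of at least 1.0 and platelets of at least 100 (× 10⁹/L).
- SAP section 2.2.2: CR is scored over Cycle 1.
- Protocol section 4.5.2: Cycle 1 ends at Day 28, or at the day of best count recovery up to Day 56.
- Protocol section 5.1.1.2: in responders to the combination in the earlier AML study, mean recovery was 34 days, which lies inside that window.

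So in a CR any return of the counts to these levels belongs to Cycle 1, before Cycle 2 Day 1. CRp, and CRi with low platelets, lack platelet recovery by definition, and CRi may have ANC below 1.0. Some of these patients have no Cycle 1 crossing to find.

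**2. The rule applied to an invented platelet series** (an assumption, not trial data). Cycle 2 Day 1 is Day 36.

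| Day | 1 | 8 | 15 | 22 | 28 | 34 | 36 | 43 | 50 | 57 | 64 | 71 |
|---|---|---|---|---|---|---|---|---|---|---|---|---|
| Platelets | 60 | 25 | 10 | 30 | 80 | 120 | 130 | 90 | 40 | 60 | 105 | 140 |

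- First upward crossing of 100 within the interval: Day 34.
- First upward crossing of 100 after the interval: Day 64, which is recovery from the Cycle 2 fall. The difference is 64 − 34 = 30 days, with the clock running from the first dose in both cases.
- Same patient without Cycle 2, series ending on Day 34: the within-interval rule gives Day 34. Under the SAP text, if the latest Cycle 1 value only closes the interval, as it does in the nadir paragraph, there is no recovery. If it is the recovery assessment, the time is the date of the last Cycle 1 count. That equals the first crossing here only because the series stops on that day.

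Patients with and without a Cycle 2 Day 1 value are thus handled by different rules on either reading of the fallback.

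**3. How many CRs are in play.** Inputs from SAP sections 2.3 and 3.1: 440 patients, 85% TP53 wild type, 2:1 allocation, CR probabilities 0.323 and 0.16.
- Wild type: 440 × 0.85 = 374.
- Idasanutlin arm: 374 × 2/3 = 249.3; expected CRs 249.3 × 0.323 = 80.5.
- Control arm: 374 × 1/3 = 124.7; expected CRs 124.7 × 0.16 = 19.9.
- Total: 80.5 + 19.9 = 100.4, about 100.

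The documents do not say how many of these will have a Cycle 2 Day 1 value. Among the wild-type CRs, the number whose Cycle 1 recovery is missed lies between 0 and about 100 if the fallback value counts as the recovery assessment. It is about 100 if that value merely closes the interval. CRp, CRi and TP53-mutant responders are additional, and the plan gives no rates for them.

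**4. The transfusion rule.** It does not name the product. Protocol Appendix 14 recommends platelet transfusion for very low counts or bleeding, and red cells to maintain hematocrit or hemoglobin. As worded, a red-cell transfusion given for hemoglobin could remove a patient from the neutrophil summary.

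**The case against.** The strongest reply is that this is a drafting slip and that Cycle 1 recovery was always meant. The wording speaks of counts coming back up, the nadir is defined on the same interval, the clock starts at first dose, and the 34-day figure from the earlier study looks like the same kind of measure. This is plausible. But the analysis will be programmed from the text, and the text does not say it.

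A reader might infer that Cycle 1 recovery is never counted for anyone. The documents do not support that: the fallback uses a Cycle 1 value when there is no Cycle 2 Day 1 value, and the analysis set includes CRp and CRi patients who may not have recovered in Cycle 1.

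A reader might also infer that the transfusion rule removes the slowest recoverers, or that the arms will differ through unequal uptake of Cycle 2. Either could happen, but no figure in the documents shows it. The exclusion is triggered only by the 24 hours before one assessment, and guarding against transfusion-supported counts is reasonable. What remains is narrower: the SAP drops the patient instead of the value, and does not tie the transfusion type to the count.

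Finally, thrombocytopenia is also covered by graded laboratory summaries, shift tables and nadir analyses in section 4.7.3, and by the analyses of adverse events of special interest in section 4.7.2. That limits the consequence but does not make the recovery summary correct.

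**Conclusion.** The point holds as a defect of definition. Followed as written, section 4.7.3 gives wrong recovery times for responders who recovered in Cycle 1 and have a Cycle 2 Day 1 value. It measures responders without that value by another rule, and it selects patients on a post-baseline event related to the outcome. The 30-day discrepancy is an illustration that rests on the invented series; it is not an estimate of bias. The number of patients affected, the net direction and any between-arm effect cannot be established from the documents.

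The impact is confined to a descriptive safety summary in responders. The primary and secondary efficacy endpoints, alpha and power are untouched. This is a minor correction, worth making because it costs so little.

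**What to change.** Reword the recovery paragraph in SAP section 4.7.3 as follows.

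- Define time to recovery as the time from first study drug to the first count over the threshold after the Cycle 1 nadir, including values within Cycle 1. Apply this to all responders, whether or not they receive Cycle 2.
- Disregard platelet values within 24 hours after a platelet transfusion and keep the patient. Do not apply the transfusion rule to neutrophils.
- State the Kaplan-Meier censoring rule for patients who do not recover, for example at the last Cycle 1 count before Cycle 2 or HSCT. Note beside it that censoring at the start of Cycle 2 may be informative for CRp and CRi patients, who can begin Cycle 2 without full recovery (protocol section 4.3.2.4).
- While editing, align the platelet threshold: the SAP requires a value over 100, whereas CR requires at least 100.

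The cost is SAP text and programming. Protocol Appendix 1 already schedules hematology on Days 8, 15, 22 and 28 of Cycle 1, then weekly up to Day 56 when recovery is incomplete. Protocol section 4.4.1 already requires blood products to be recorded.

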### **3.4 OUTCOME MEASURES**

#### **3.4.1 Efficacy Outcome Measures**

The efficacy outcome measures for this study are:

- OS
- EFS
- DOR
- CR
- CRp
- CRi
- Overall remission rate (ORR) (CR, CRp, and CRi)
- *Allogeneic* HSCT

*For definition of response criteria (CR, CRp, CRi), see Section 4.5.8; for all other definitions, see Section 6.4.*

In this study, CR or CRp achieved by induction Cycle 1 must be confirmed for the purpose of the *futility* interim analysis.

For all patients in CR or CRp who do not proceed to Cycle 2, an additional HMRA will be scheduled 30 ( $\pm$ 3) days after the previous HMRA performed at the end of Cycle 1 (Note that this assessment will not be required after the *futility* interim analysis). For all patients proceeding to Cycle 2, the HMRA at the end of Cycle 2 will be used as the confirmatory response in the analysis. If a patient proceeds directly to HSCT in aplasia after Cycle 1 or prior to undergoing an HMRA, this will be considered confirmed CR *for the purpose of futility analysis* unless the HSCT was clearly performed in disease progression or relapse.

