#### **4.3.2.4 Guidelines for Consolidation Therapy (Cycles 2 and 3)**

Responding patients (CR/CRp or CRi with neutrophil recovery [ $\geq 0.5 \times 10^9/L$ ]) who do not proceed to transplant, directly or at all, are recommended to continue with consolidation therapy with cytarabine and idasanutlin or placebo for a maximum of two additional cycles if not medically contraindicated. Mandatory prophylaxis must be adhered to in the same manner as in Cycle 1.

Continuation of study medication into consolidation therapy is determined based on the presence of clinical response at the end of Cycle 1 (see [Appendix 4](#)). Once CR/CRp/CRi with neutrophil recovery ( $\geq 0.5 \times 10^9/L$ ) is observed, consolidation therapy should begin within 7 days from the day that clinical response is observed. If Cycle 2 is started  $>7$  days after clinical response is observed (e.g., due to prolonged toxicity), weekly blood counts must be performed to confirm that the patient remains in clinical remission. If relapse is suspected, a bone marrow aspirate must be taken and an HMRA performed as an unscheduled assessment. These same rules apply when patients move from Cycles 2 to 3.

It was observed in Study NP28679 that patients who continued on full doses of treatment following achievement of CR frequently required additional time for blood count recovery. Therefore, the daily dose of idasanutlin/placebo (300 mg BID in Cycle 1) will be reduced to 50% (300 mg QD for subsequent cycles) for consolidation because a 50% dose reduction was tolerated for multiple cycles in leukemia patients with a minimum of dosing delays.

- Patients with CR at the Day 28 HMRA may proceed immediately to consolidation therapy with 50% idasanutlin (300 mg QD in the morning) and 100% cytarabine (1 g/m^2).
- For patients with CRp/CRi at the Day 28 weekly blood counts should be obtained between the Day 29 and Day 42. As soon as blood counts recovered and CR/CRp is observed (but latest at Day 42), patients may start Cycle 2 with 50% idasanutlin (300 mg QD in the morning) and 100% cytarabine (1 g/m^2).

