#### 4.5.8 Hematologic Malignancy Response Assessment

The following criteria should be used to determine hematologic malignancy response (Cheson et al. 2003; Döhner et al 2017; NCCN guidelines):

- CR: Bone marrow blasts < 5%, absence of blasts with Auer rods; absence of extramedullary disease; ANC  $\geq 1.0 \times 10^9/L$ ; platelets  $\geq 100.0 \times 10^9/L$
- CRi: All CR criteria except for residual neutropenia (ANC <  $1.0 \times 10^9/L$ ) or thrombocytopenia (platelets <  $100.0 \times 10^9/L$ )
- CRp: All CR criteria except for thrombocytopenia (platelets <  $100.0 \times 10^9/L$ )
- Treatment failure:
  - Resistant disease:  
Failure to achieve CR, CRi, or CRp; only includes patients surviving  $\geq 7$  days following completion of initial treatment, with evidence of persistent leukemia by blood and/or bone marrow examination.
  - PR and SD/hematologic improvement (HI) will be considered treatment failure.
    - PR  $\geq 50\%$  decrease in bone marrow blasts
    - SD/HI = decreased peripheral blast percentage, decreased frequency of transfusions, improvement in peripheral cell counts
  - Death in aplasia:  
Deaths occurring  $\geq 7$  days following completion of initial treatment while cytopenic; with an aplastic or hypoplastic bone marrow obtained within 7 days of death, without evidence of persistent leukemia
  - Deaths from indeterminate cause:  
Deaths occurring before completion of therapy, or < 7 days following its completion; or deaths occurring  $\geq 7$  days following completion of initial therapy with no blasts in the blood, but no bone marrow examination available
- Relapse of Disease:  $\geq 5\%$  bone marrow blasts; or reappearance of blasts in the blood, or development of extramedullary disease.

HMRAs require sampling of blood and bone marrow as indicated. Bone marrow aspirates are required, but if bone marrow biopsies are performed, the biopsy results should be provided. Depending on timepoint in the schedule of assessments the HMRA is established based on blood counts only, or includes the assessment of bone marrow. Patients will be considered to be in their best response state until definitive evidence of relapse is available from blood counts, bone marrow aspirate, or bone marrow biopsy.

In the event that a bone marrow aspirate or biopsy is equivocal (i.e., a recovering marrow), the bone marrow assessment and complete blood count should be repeated > 7 days later.

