## **4. STATISTICAL METHODS**

Except where specified otherwise, continuous data will be summarized with descriptive statistics (number of non-missing data, mean, standard deviation, median, minimum, and maximum). Categorical parameters data will be described using frequencies and percentages.

Descriptive summaries will be provided by treatment group. The main treatment comparison is between idasanutlin+cytarabine and placebo+cytarabine in *TP53* WT patients and all patients who have been randomized. All the statistical tests will be 2-sided.

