##### **4.7.2 Adverse Events**

Coding of adverse events will be done using the most recent version of the Medical Dictionary for Regulatory Activities (MedDRA). All adverse events and

laboratory parameters will be assessed according to the National Cancer Institute Common Terminology Criteria for Adverse Event (NCI CTCAE) version 4.03 grading system.

All adverse events will be reported from the day of first study treatment. All adverse events will be displayed by body system (system organ class), NCI CTCAE grade, and relation to study treatment. All serious adverse events, Grade  $\geq 3$  adverse events, adverse events leading to death, adverse events leading to study treatment modification, adverse events leading to study treatment discontinuations, and adverse events leading to early study withdrawals will be summarized by treatment arm.

Deaths and reason for deaths reported during the study will be summarized by treatment arm. Deaths occurring within 30 and 60 days after randomization will also be summarized.

In the summary tables showing the overall incidence of adverse events, patients who experienced the same event on more than one occasion will be counted only once in the calculation of the event frequency. The adverse event with the most extreme intensity will be used for reporting.

Additional analyses will be performed by treatment arm based on the selected adverse events of special interest, which are defined in the study protocol, as well as based on any adverse event, which might require further investigation. Analyses of the time to onset of these adverse events will be performed. Time to adverse events will be listed. Patients without an adverse event will be censored at last date known to be alive.

In order to account for potential differences in the duration of adverse event reporting between treatment groups, an exploratory analysis of selected adverse events by duration of exposure might be performed based on adverse event rates adjusted for patient-years at risk when enough events are observed.

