For physical function and global health status/QoL, higher scores are reflective of better HRQoL and a clinically meaningful improvement is defined as at least a 10-point increase. For fatigue, lower scores are reflective of less fatigue and a clinically meaningful improvement is defined as at least a 10-point decrease. Conversely, clinically meaningful deterioration is defined as at least a 10-point decrease and 10-point increase, respectively.

Time to deterioration is defined as the time from randomization to the first documentation of a 10-point decrease in EORTC QLQ-C30 physical functioning and global health status and a 10-point increase in fatigue from baseline. Time to

improvement is defined as the time from randomization to the first documentation of a 10-point increase in EORTC QLQ-C30 physical functioning and global health status and a 10-point decrease in fatigue from baseline.

Time to deterioration and time to improvement will be displayed using Kaplan Meier curves. Patients who do not have an observed deterioration or improvement, respectively, at the time of clinical data cut-off will be censored at the last non-missing assessment date. Patients without a post-baseline assessment will be censored at randomization.

The EQ-5D-5L questionnaire consists of two components: the EQ-5D-5L descriptive system, which has 5 dimensions (mobility, self-care, usual activities, pain/discomfort, and anxiety/depression) with five levels (no problems, slight problems, moderate problems, severe problems, and extreme problems) and a visual analogue scale (EQ VAS) ranging from 0 (worst possible health state) to 100 (best possible health state), which measures an overall health state.

The EQ-5D-5L health states, which are defined based on the EQ-5D-5L descriptive system, will be converted into a single index value according to the EQ-5D-5L guidelines ([van Reene and Janssen 2015](#)). The EQ-5D-5L single index value will be calculated using the United Kingdom preference weights. Descriptive statistics (mean, standard deviation, median, minimum, and maximum) and change from baseline will be presented by treatment arm and at each timepoint.

Data from the EQ-VAS will be used to assess the overall health status. Descriptive statistics (mean, standard deviation, median, minimum, and maximum) and change from baseline at each timepoint will be displayed by treatment arm.

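### The time-to-recovery summary statistics and boxplots in SAP 4.7.3 drop responders whose counts never recover, and the Kaplan-Meier beside them has no censoring rule

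*SAP*

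**What the plan says.** SAP 4.7.3 defines recovery as the count crossing back over 100 for platelets, or over 0.5 or 1 for neutrophils. It places the crossing after the interval from Cycle 1 Day 1 to predose Cycle 2 Day 1, and selects the latest Cycle 1 value if there is no Cycle 2 Day 1 value. The only stated exclusion is a transfusion in the 24 hours before the selected assessment. The section then plans: "For responders only (CR, CRp, CRi), summary statistics and boxplots for time to recovery (in days) for both neutrophils and platelets will be produced", by arm, "as well as Kaplan Meier for time to recovery starting on study drug first administration".

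The general rule in SAP 4 is that "continuous data will be summarized with descriptive statistics (number of non-missing data, mean, standard deviation, median, minimum, and maximum".

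Protocol 4.5.8 fixes who is in the responder set. One line reads "CRp: All CR criteria except for thrombocytopenia", so a CRp patient has platelets below 100 at that response. CRi allows either neutrophils below 1.0 or platelets below 100.

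Elsewhere the SAP does state censoring. For time to adverse event (4.7.2): "Patients without an adverse event will be censored at last date known to be alive". For the quality-of-life endpoints (4.8.1), patients without the event "will be censored at the last non-missing assessment date". OS, EFS, DOR and LFS also have rules. Recovery has only a time origin, and the missing-data section (4.10) adds nothing for it.

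**The concern.** Time to recovery exists only for patients who recover. The analysis set deliberately includes responders who may not have done so, and nothing brings them into the mean, median or boxplot. The more slowly an arm recovers, the more of its slow patients are removed, so a real delay shrinks in these displays.

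The Kaplan-Meier is the natural remedy, but its upper part depends on a choice the SAP does not make. Protocol 4.3.2.4 says of patients in CRp or CRi at Day 28: "As soon as blood counts recovered and CR/CRp is observed (but latest at Day 42), patients may start Cycle 2". A patient can therefore begin a second myelosuppressive course with platelets still below 100. One analyst would censor at that point; another would wait for a crossing that then reflects Cycle 2 treatment.

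The displays have a purpose. Protocol 5.1.1.2 names a longer period of aplasia as a possible effect of the combination, and Protocol 4.4.2.3 bases the anticoagulant restriction on potentially long thrombocytopenia while calling the clinical data limited. The 34-day Phase I figure quoted in both sections is itself a Kaplan-Meier estimate, so a mean over recovered patients is not comparable with it.

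**Working it through.** The documents give no figure for this analysis, so there is none to reproduce. The exclusion follows from the text; its size needs assumptions.

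**Who drops out.** SAP 4.4.2 takes response as the best assessment over Cycle 1. If that classification is used here, a patient left at CRp did not meet the platelet threshold at any Cycle 1 response assessment. CRp meets every other CR criterion, so neutrophils are at least 1.0. Only CRi can lack neutrophil recovery. In the Phase I combination patients (Protocol 1.2.1.1), CR/CRp was 21 of 75 and CR/CRp/CRi was 22 of 75, so CRi added 22 − 21 = 1 of 22 responders. The CRp share of the 21 is not given.

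**The latest-value sentence.** It parallels the nadir rule in the same section, where the latest value closes the interval. If it were instead read as an entry for unrecovered patients, it would give them a recovery date on which they had not recovered.

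**Inputs for size.**
- From the documents: a mean of 34 days in patients who responded to idasanutlin plus cytarabine (Protocol 4.4.2.3, 5.1.1.2); counts followed to Day 56 if unrecovered (Protocol 4.3.2.4, Appendix 1); Day 42 as the latest Cycle 2 start for CRp patients.
- Assumed: lognormal recovery times, log-SD s = 0.35, control 1.2 times faster, and a crossing during Cycle 1 counts as recovery.

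**Formulas.** Median m = mean / exp(s²/2). Share recovered by day c: P = Φ(ln(c/m)/s). Median among the recovered only: m·exp(s·Φ⁻¹(P/2)).

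**True medians.** Idasanutlin: 34/exp(0.06125) = 31.98. Control: 31.98/1.2 = 26.65. True gap: 5.33 days.

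**Counts end at Day 56.**
- Idasanutlin: P = Φ(1.601) = 94.5%; recovered-only median 31.98·exp(0.35 × −0.0686) = 31.22.
- Control: P = Φ(2.122) = 98.3%; recovered-only median 26.65·exp(0.35 × −0.0212) = 26.45.
- Shown gap 4.77 days; left out 5.5% vs 1.7%.

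**Counts end at Day 42.**
- Idasanutlin: P = Φ(0.779) = 78.2%; recovered-only median 29.03.
- Control: P = Φ(1.300) = 90.3%; recovered-only median 25.54.
- Shown gap 3.49 days; left out 21.8% vs 9.7%.

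The Day 42 case is a bound: only patients who start Cycle 2 then stop being informative then.

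**Sensitivity.** With log-SD 0.5 the true medians are 30.0 and 25.0 (gap 5.0), shown as 3.9 days (Day 56) or 2.8 days (Day 42). For a single arm with a true median of 34 days and log-SD from 0.3 to 0.7, the recovered-only median is 33.4 down to 27.5 days (Day 56), or 31.0 down to 24.0 days (Day 42). The direction is the same throughout.

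**The case against.** The strongest reply is that little is hidden. The number of non-missing values is reported, SAP 4.4.2 tabulates CR, CRp and CRi by arm, and 4.7.3 adds laboratory grades and shift tables. The planned Kaplan-Meier is the display comparable with Phase I, and in the cases examined its median does not depend on the censoring choice. Haematology also continues after Cycle 1, so some patients cross later. This limits the harm and stands as a reason to rate the point low. It does not make the recovered-only medians and boxplots right, and a crossing after Cycle 2 begins measures something else.

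Four stronger readings are tempting and are not supported.
- A reader might put the 34-day mean on the control arm and make idasanutlin 20% slower. The same formulas then turn a true gap of 6.4 days into 2.9 (Day 42) or 4.9 (Day 56), with 22% vs 40% or 6% vs 14% left out. The documents place the 34 days on the combination.
- A reader might treat neutrophils and platelets alike. The response definitions and the Phase I counts say otherwise.
- A reader might cite the Protocol 3.4.1 provision beginning "If a patient proceeds directly to HSCT in aplasia after Cycle 1 or prior to undergoing an HMRA" as showing unrecovered responders. It counts such patients as confirmed CR for the futility analysis only; otherwise Protocol 6.4.2 treats patients without a response assessment as non-CR.
- A reader might put percentages on the effect of the missing censoring rule. That needs rates of Cycle 2 start, transplant and death before recovery, which the documents do not give.

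Restricting to responders is itself defensible, since Protocol 5.1.2.2 ties marrow recovery to blast clearance.

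**Conclusion.** The point holds as a minor one. Following SAP 4.7.3 as written biases the summary statistics and boxplots towards faster recovery, chiefly for platelets in CRp and CRi patients, and leaves the Kaplan-Meier open to more than one construction. The exclusion of unrecovered responders is inferred from the definition and the non-missing rule; the SAP does not state it in words.

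Under the main assumptions the loss is about half a day of a 5.3-day median gap with a Day 56 end, and just under 2 days with a Day 42 end. The distribution, its spread and the ratio between arms are assumed; only the 34 days and the two day limits come from the documents. No hypothesis test, alpha, power or stopping rule depends on these displays. A reader should not infer that the planned Kaplan-Meier is wrong: with a proper rule it would show slower recovery correctly.

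**What to change.** Amend SAP 4.7.3 in four places.

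1. **Definition.** *Time from first study drug administration to the first count over the threshold after the nadir, within the interval from Cycle 1 Day 1 to predose Cycle 2 Day 1 (or the last Cycle 1 count if there is no Cycle 2).* This has to change together with the censoring rule. The present wording puts the crossing after that interval, so censoring at Cycle 2 would leave no possible event for patients who continue.
2. **Counts.** Report responders recovered and not recovered, by arm and by lineage.
3. **Quantiles.** Take the median, quartiles and recovery probabilities at Days 28, 42 and 56 from the Kaplan-Meier. Censor unrecovered responders at the last count before the earliest of Cycle 2 start, HSCT conditioning, new anti-leukemia therapy or relapse, or otherwise at the last Cycle 1 count (up to Day 56), and tabulate the reasons. Count death before recovery separately, as a competing event; if any occur, the recovery probabilities should come from a cumulative incidence estimate.
4. **Boxplots.** State the number not recovered on each.

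The cost is SAP wording. Protocol Appendix 1 already schedules weekly counts to Day 42 or Day 56 and the collection of survival, transplant and later therapy. There are two drawbacks. Censoring at Cycle 2 or transplant may be informative, which is why the reasons are listed, and an upper quartile may not be estimable if too few patients recover.
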